## 1 Introduction

---

CooperVision (CV) produces a number of contact lens products including the MyDay brand. All MyDay Sphere lenses and MyDay Energys lenses feature CooperVision's exclusive Smart Silicone Technology. This combination of material technologies provides a contact lens with high oxygen permeability that is naturally wettable and offers unique comfortable experience.

This study is designed to evaluate how habitual or adapted wearers of MyDay Sphere lenses will perform following a refit with Comfilcon A aspheric lenses, a novel soft contact lens with digital zone optics design, over one week of daily wear. Lens wear experience overall and during digital device use will be assessed.

## 2 Study Objective

---

[figure not shown]
The aim of this study is to determine if habitual or adapted wearers of MyDay Sphere lenses can be confidently refit into MyDay Energys lenses and be successful after one week of daily wear.

**Primary outcomes:**

- Overall lens fit acceptance grade (Appendix 9)

**Secondary outcomes:**

- Lens centration & lens movement (Appendix 9)

## 3 Study Hypothesis

---

### 3.1 Study Hypothesis

- Null hypothesis (Ho): There is no difference in overall lens fit acceptance grade between MyDay Sphere and MyDay Energys lenses for the key variables measured.
- Alternative hypothesis (H1): There is a difference in overall lens fit acceptance grade between MyDay Sphere and MyDay Energys lenses for the key variables measured.

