### 5.1 Sample Size Calculation

A sample size calculation was made based on the primary outcome variable of lens fit acceptance grade, using data from a previous study: EX-MKTG-63. In this previous study the lenses compared were Biofinity and Biofinity Energys and for lens fit acceptance the difference between mean results

was 0.16, with a standard deviation of not greater than 0.4. For alpha 0.05, a sample size of 73 provides power of 92%. This variable will be graded using a 0-4 scale with 0.5 steps. Therefore, to allow for drop-outs and protocol deviations affecting inclusion in the analysis cohort, dispensing to 80 participants will be targeted.

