#### **Inclusion criteria**

A person is eligible for inclusion in the study if he/she:

- Is between 18 and 35 years of age (inclusive)
- Has read and signed the informed consent letter
- Is willing and anticipated to follow instructions and maintain the appointment schedule
- Habitually wears soft spherical contact lenses with a power between -1.00D to -6.00D (inclusive) for a minimum 5 days per week, 10 hours per day and anticipates no difficulty wearing contact lenses for 7 days per week, 10 hours per day.
- Habitually wears or is able to be adequately refit into MyDay Sphere lenses
- Demonstrates an acceptable fit with the study lenses
- Is correctable to a distance visual acuity of 0.20 logMAR (approximately 20/30) or better (in each eye) with the study contact lenses
- Uses digital devices, (e.g. computer, tablet, smart phone, iPad), for more than 4 hours a day, 5 days a week.
- Manifest cylindrical spectacle refraction does not exceed -0.75DC in either eye
- Has clear corneas and no active ocular disease
- Has a contact lens refraction that fits within the available parameters of the study lenses.

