### 9.2.1 Contact lenses

All subjects will be trial fitted and, if suitable, dispensed the MyDay Sphere and the MyDay Energys lens brand. The study lenses will be provided by the Sponsor. Details of the contact lenses are shown in Table 1.

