#### 9.3.4 Visit 4: Fit and Dispense MyDay Energys

Visit 4 occurs after Baseline MyDay Sphere data have been collected. At this visit, MyDay Energys will be fit dispensed. The following procedures will be conducted:

- Changes to health or medication (not required if completed on same day already)

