### **11.1 Statistical analysis**

---

Descriptive statistics will be provided on information regarding baseline variables (e.g., age, gender). Differences between lenses and over time will be compared using Paired t-tests. Paired t-tests /analysis of variance for normal (interval/continuous) data. The appropriate test will be selected based on tests of normality. Means and standard deviations will be provided for each variable.

All participants who were evaluated will be used in the analysis. In the event of missing data, individual data points will be excluded in the analysis and not extrapolated from the collected data.

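### The objective is a successful refit, but the plan tests only for a difference, with no margin, interval criterion or visible definition of success; the primary grade also uses two step sizes

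*Combined protocol and SAP*

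**What the plan says.** Section 2 sets the aim: to determine whether wearers "can be confidently refit into MyDay Energys lenses and be successful after one week of daily wear". The primary outcome is the overall fit acceptance grade. Its definition is referred to Appendix 9, which is not in the text available.

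Section 3.1 states "Null hypothesis (Ho): There is no difference in overall lens fit acceptance grade between MyDay Sphere and MyDay Energys lenses". The alternative is a difference, with no direction given.

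Section 5.1 takes its planning difference from an earlier study of another lens pair (Biofinity and Biofinity Energys). That difference "was 0.16, with a standard deviation of not greater than 0.4. For alpha 0.05, a sample size of 73 provides power of 92" per cent. Dispensing to 80 is targeted to cover losses.

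Section 11.1 says "Differences between lenses and over time will be compared using Paired t-tests", with analysis of variance also named, the choice resting on normality tests, and means and standard deviations reported. It adds "All participants who were evaluated will be used in the analysis" and leaves missing data points out.

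Three other places bear on success:

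- The inclusion criteria require that a participant "Demonstrates an acceptable fit with the study lenses".
- Section 9.2.1 says "All subjects will be trial fitted and, if suitable, dispensed the MyDay Sphere and the MyDay Energys lens brand".
- At Visits 2, 3 and 5 a grade of 2 or lower prompts the investigator to record a reason.

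None of these is linked to the objective as a decision rule.

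The step of the 0-4 grade is 0.5 in section 5.1, at Visit 2 (9.3.2) and at Visit 3 (9.3.3). At Visit 5 (9.3.5), where Energys is graded, it is 1.

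**The concern.** The objective is a claim of acceptability, and a test of no difference does not decide such a claim in either direction. Failing to reject does not show that the lenses fit alike. Rejecting shows only that the means differ: a small significant deficit might be acceptable, and a significant gain does not say how many wearers succeeded.

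Table 1 gives both lenses the same material, base curve and diameter, so similar fit is plausible and a non-significant result is a likely outcome. The sponsor would then have no criterion, fixed in advance, for calling the refit acceptable. Section 9.2.7 leaves participants and investigators unmasked, so a margin or threshold chosen after the grades are seen would carry little weight.

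The step conflict affects the same comparison. If Energys is graded only in whole units, someone graded 3.5 with Sphere whose fit is unchanged cannot be recorded at 3.5 with Energys.

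**Working it through.** **Inputs.** From section 5.1: n = 73, difference 0.16, standard deviation at most 0.4, alpha 0.05, stated power 92%. The section does not say whether 0.4 refers to paired differences; that reading is assumed because it reproduces the stated power. The margins below are assumptions, since the plan gives none.

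**1. The plan's own figure.** Two-sided paired t-test, 72 degrees of freedom, noncentrality = (0.16/0.4) × √73 = 3.42. Power is 92.1%, which matches. A one-sided test at 0.05 would give 95.9%, so the calculation is two-sided, as the hypothesis wording implies. This is power to detect a difference.

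**2. Chance of a non-significant result.** Same test, noncentrality = (true deficit/0.4) × √73.

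| True deficit of Energys | Chance of non-significance |
|---|---|
| 0 | 95% |
| 0.05 | 82% |
| 0.10 | 44% |
| 0.16 | 8% |

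**3. What a non-significant result would exclude.** The 95% half-width is t(0.975, 72) × 0.4/√73 = 0.0933. The largest observed deficit that is still non-significant is 0.0933, so the interval then reaches −2 × 0.0933 = −0.187. This takes the observed standard deviation to be 0.4. At 0.3 the limit is −0.140.

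If 0.4 is instead the standard deviation of grades for each lens, that of the differences is 0.4 × √(2(1 − ρ)). The half-width is then 0.132 at ρ = 0, 0.093 at ρ = 0.5 and 0.066 at ρ = 0.75.

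**4. Power for a margin-based criterion.** Non-inferiority at one-sided 0.025, n = 73, standard deviation 0.4, noncentrality = ((M − true deficit)/0.4) × √73.

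| Assumed margin M | No true difference | 0.05 worse | 0.10 worse |
|---|---|---|---|
| 0.16 | 92% | 64% | 24% |
| 0.20 | 99% | 89% | 56% |
| 0.25 | over 99% | 99% | 89% |

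**5. Grading step.** Rounding a half grade to a whole grade moves one participant by 0.5. As an illustration, if a share f of participants lay at a half grade at Visit 5 and all were rounded the same way, the mean would shift by 0.5f. A shift equal to the planning difference needs f = 0.16/0.5 = 32%. Rounding in both directions would largely cancel in the mean but add noise.

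**The case against.** **The trial is informative as it stands.** This is correct. A bound of 0.187 is less than half of a 0.5 step, and for a margin near 0.25 the planned size is ample. A reader might infer that the study is too small or that a null result would be worthless; the figures support neither. The interval can be computed from the planned data. What cannot be recovered afterwards is a criterion fixed in advance.

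**Nowhere does the plan say that non-significance will be read as success.** Also correct. A reader might infer that intention from the pairing of aim and hypothesis, but the text does not state it. A significant result favouring Energys would lend the objective some support, and section 5.1 does not give the direction of the 0.16. The gap is that no result of the test is tied to the objective.

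**A definition of success may lie in unseen text.** Appendix 9 is unavailable and parts of Visits 4 and 5 are redacted, so that part of the point holds only for the visible text. Sections 3.1, 5.1 and 11.1 show no redaction, so the absence of a margin or interval criterion from them stands.

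**Failed refits are screened out before Energys is tried.** A reader might infer this because eligibility is confirmed at Visit 1, while section 9.3.4 says "Visit 4 occurs after Baseline MyDay Sphere data have been collected". The documents do not settle it. Table 2 allows a longer Visit 1 when both lenses are fitted, and parts of Visits 1 and 4 are redacted. Section 12.1 also plans a discussion to confirm the analysed cohort. What remains is narrower: a participant with no Visit 5 grade drops out of the paired comparison, which matters if a success proportion is reported.

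**Conclusion.** The mismatch is real and should be fixed, but it is not fatal. The hypothesis, sample size and analysis sections support a two-sided test of difference only, and no criterion in them answers the question in section 2. The stated power is arithmetically right for the test it describes.

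The size rests on 73 evaluable participants and a standard deviation of paired differences of 0.4. On those terms non-significance is more likely than not at a true deficit of 0.05 and close to even at 0.10, while deficits beyond about 0.187 would be excluded. Whether a deficit of that order is acceptable is for the sponsor to say; the documents do not.

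The step conflict is a separate inconsistency in the primary outcome. Its effect on the result cannot be sized from the documents, which do not show the case report form.

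**What to change.** Before data are reviewed:

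1. Reconcile the step for overall fit acceptance across 5.1, 9.3.2, 9.3.3 and 9.3.5, so that both lenses are graded on one scale.
2. In 11.1, report the mean paired difference (Energys at Visit 5 minus Sphere at Visit 3, one value per participant) with its 95% confidence interval.
3. In 3.1 and 11.1, pre-specify a criterion that the sponsor justifies. It can be a margin M, met when the lower confidence limit lies above −M, or a success proportion at a stated grade with an exact confidence interval and a threshold. Keep the difference test as secondary.
4. In 5.1, restate the power for that criterion at 73 evaluable participants, giving the assumed true difference or success rate.
5. If a success proportion is used, count as non-successes the participants dispensed or attempted with Energys who could not be fitted or who stopped for lens-related reasons. Show all losses counted as failures only as a labelled worst case. State at which visit the acceptable-fit criterion is applied to Energys.

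The cost is text, with no added assessments. The sponsor must commit to a margin or threshold, and the stated power may become less favourable. More participants would be needed to keep about 92% power if the margin is below about 0.16, or if a true deficit is expected and the margin is tight.

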## 4 Study Design

---

This is a prospective, multi-center, open label, bilateral wear, one week dispensing study comparing the clinical performance of the MyDay Sphere lenses following a refit with MyDay Energys lenses.

Habitual wearers of MyDay Sphere lenses will be reviewed at Visit 1 to ensure optimal visual acuity is being achieved. If the visual acuity and power of the habitual MyDay Sphere lens is optimal, the participant will continue to wear MyDay Sphere in the same prescription for at least 7 days after which baseline variables will be collected. If an amendment of the power of the habitual MyDay Sphere is required, participants will be dispensed with the new power of the MyDay Sphere lenses to be worn for at least 7 days. In the instance where the participant habitually wears lenses which are not MyDay Sphere, the participant will be fit and dispensed MyDay Sphere lenses to be worn for at least 7 days.

After wearing MyDay Sphere lenses for at least 7 days in the study, all participant will return for baseline variables to be evaluated and will be then be dispensed with MyDay Energys. The participant will be asked to return for evaluation after 7-10days of lens wear. Participants will exit the study following the final evaluation of MyDay Energys.

This study will be open label. Over labeling of the blister packs is not required.

[figure not shown]

Figure 1 Study flow chart.

[figure not shown]

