### **9.2.7 Masking and Control of Study Materials**

The study contact lenses will be not be masked to the participant. Study lenses will be dispensed in blisters without the lens box. The investigator will not be masked.

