### 9.3.2 Visit 2: Dispense MyDay Sphere

- Insert MyDay Sphere lenses (For habitual MyDay wearers, ensure to use updated power if an overrefraction was found)
  - [REDACTED]
  - [REDACTED]
- Fit assessment of MyDay Sphere
  - Centration: Optimum, decentration acceptable, decentration unacceptable
    - [REDACTED]
    - [REDACTED]
  - Post-blink lens movement, 0-4, 1 step, 0 = Insufficient, unacceptable movement
    - [REDACTED]
  - Overall fit acceptance 0-4, 0.5 step, 0 = Should not be worn
    - If overall fit acceptance  $\leq$  2, provide reason
- Provide sufficient MyDay Sphere to wear daily for at least 7 days
- After at least 7 days of MyDay Sphere, participant returns for Visit 3 wearing MyDay Sphere for at least 2 hours on that day
  - [REDACTED]

[figure not shown]

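### Section 3.1 tests a difference between lenses, but the fixed Sphere-then-Energys order with an unmasked grader supports only a before-after statement about refitting

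*Combined protocol and SAP*

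**What the plan says.** - **Hypothesis (3.1).** The null is no difference in grade between the two lenses. The alternative is: "There is a difference in overall lens fit acceptance grade between MyDay Sphere and MyDay Energys lenses for the key variables measured". Table 1 labels Sphere as control and Energys as test.
- **Sequence (section 4).** After at least 7 days on Sphere, "all participant will return for baseline variables to be evaluated and will be then be dispensed with MyDay Energys". They are reviewed on Energys 7-10 days later. No randomised or reversed order and no parallel group is described.
- **Masking (section 4 and 9.2.7).** "This study will be open label", and "The investigator will not be masked".
- **Outcome (section 2).** The primary outcome is the overall fit acceptance grade, given by the investigator on a 0-4 scale.
- **Analysis (11.1).** "Differences between lenses and over time will be compared using Paired t-tests". The visits are not named, there is no order or period term, and no rule is given for interpreting the result.
- **Aim (section 2).** The aim is whether Sphere wearers can be refit into Energys and succeed after a week.

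**The concern.** The aim describes what happens after a refit. The hypothesis attributes a difference in grade to the lens. A fixed sequence can serve the first but not the second.

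The outcome is a judgement made by someone who knows which lens is on the eye. Table 1 gives both lenses the same material, water content, base curve and diameter, and the difference planned for in 5.1 is only 0.16 grade. Shifts in grading that have nothing to do with the lens could be as large as that.

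A significant paired test would naturally be reported as a lens difference, although order or expectation could have produced it. A shift in the opposite direction could hide a real difference.

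**Working it through.** **1. Inputs.** From 5.1: mean difference 0.16, SD not greater than 0.4, alpha 0.05, n = 73, stated power 92%. Sidedness is not stated; I use two-sided. I read the SD as that of the paired differences, because that reading reproduces the plan's figure. I take the primary contrast as Visit 5 minus Visit 3, since 9.3.3 calls Visit 3 the baseline; 11.1 does not name the visits.

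**2. The plan's own figure.** SE = 0.4/√73 = 0.0468. Noncentrality = 0.16/0.0468 = 3.42. The two-sided paired t-test with 72 degrees of freedom has power 92.1%, so the stated 92% is reproduced and the sample size arithmetic is sound.

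**3. What the test estimates.** For each participant, write the difference as D = δ + π + error. Here δ is the lens effect and π is everything else that changes between the first and second period: order, time in study and grader expectation. The mean of D estimates δ + π. Because everyone has the same order, no participant contributes information on δ and π separately. This holds whatever the size of π.

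**4. How small a shift matters.** The smallest significant mean is t(0.975, 72) × SE = 1.993 × 0.0468 = 0.093 grade.

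**5. Rejection rates for an assumed shift.** The documents give no value for π, so the range is an assumption. Noncentral t, SD 0.4, n = 73:

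| Shift π | No lens effect (δ = 0): chance of p<0.05 | True δ = 0.16 with an opposite shift: power |
|---|---|---|
| 0 | 5% | 92.1% |
| 0.05 | 18.4% | 64.0% |
| 0.08 | 39.2% | 39.2% |
| 0.10 | 55.9% | 24.4% |
| 0.16 | 92.1% | 5% |

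**6. Translation into grading steps, with a caveat.** On a 0.5-step scale, 0.093/0.5 is a net half-step move in about 19% of participants, and 0.16/0.5 is one in 32%. These percentages assume the same 0.5 step at both visits. Sections 5.1, 9.3.2 and 9.3.3 give 0.5 steps, but 9.3.5 gives 1 step for Energys. As written, the grading step also changes with the lens, and these sections must be reconciled.

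**The case against.** **This is a refit study, so the order is intended.** That is right. Section 4 describes performance following a refit, and the open-label status is declared. There is also some standardisation: at least 7 days on Sphere for everyone, at least 2 hours of wear before Visits 3 and 5, and daily disposable lenses throughout. These features limit differences in adaptation and wear time. They do not remove grader expectation, and they do not make the between-lens hypothesis testable. The sequence can stay; the hypothesis should match it.

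**The shift sizes are assumed.** They are. The rejection rates illustrate sensitivity and do not predict what this trial will show. The aliasing in step 3 does not depend on them.

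Three stronger readings are tempting, and the documents do not support them.

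- *That the plan ignores its repeat Sphere grading.* Sphere fit is graded at Visit 2 and again at Visit 3, and 11.1 plans comparisons over time, which could include that pair. All that can be said is that this use is not specified.
- *That the Visit 2 to Visit 3 change measures the order effect.* Visit 2 is graded at dispensing and Visit 3 after at least 7 days, so the change mixes lens settling with regrading. Both grades are of Sphere, so it cannot capture expectation about Energys. It may also cover only some participants: a note to Table 2 makes Visit 2 conditional, while 9.3.1 sends eligible habitual Sphere wearers straight on to it. Its precision is limited too. With an assumed SD of 0.4, the 95% interval half-width is 0.093 at n = 73 and 0.128 if only 40 participants have both grades.
- *That different graders at the two visits will cost a known amount of power.* Section 6.2 provides for co-investigators, and no visible text ties a participant to one grader. But the documents give no between-grader variance, the SD of 0.4 is an upper limit that may already include it, and the text for Visits 3 to 5 is partly redacted. No power loss can be calculated from the documents.

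**Conclusion.** The point holds for the hypothesis in 3.1. Lens is completely aliased with period, the grader is unmasked, and the planned paired test estimates the sum of the two effects. The design supports a before-after statement about refitting and cannot attribute a change in grade to the lens.

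At the plan's SD of 0.4 and n = 73, an assumed non-lens shift of 0.05 to 0.10 grade gives a significant result in 18% to 56% of trials with no lens effect. A shift of the same size in the opposite direction cuts power for a true 0.16 from 92% to between 64% and 24%. These figures rest on the assumed shifts and on reading the SD in 5.1 as that of paired differences.

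The refit aim in section 2 and the power calculation are not in question. The correction is worth making because the claim as written goes beyond what the data can show, and it costs little to put right.

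**What to change.** 1. **Section 3.1.** Restate both hypotheses in terms of the change in overall fit acceptance grade after refit from Sphere (Visit 3) to Energys (Visit 5). State there, and in any conclusion drawn from the test, that lens and order cannot be separated. The cost is wording and a more modest claim; visits, sample size and sequence are unchanged.
2. **Sections 9.3.3 and 9.3.5.** Unless redacted text already does so, require the same investigator to grade a given participant at Visits 3 and 5. This removes differences between graders from the contrast, though not expectation. The cost is a small scheduling constraint.
3. **Section 11.1.** Name the visits compared. The Visit 2 to Visit 3 Sphere change may be reported descriptively where both grades exist, with its limits stated. It should not be the yardstick for the primary contrast.
4. **Reconcile two inconsistencies.** The Table 2 note and 9.3.1 differ on who attends Visit 2. Section 9.3.5 differs from 5.1, 9.3.2 and 9.3.3 on the grading step.
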